2.3 Patient disposition, demographics and other baseline characteristics

The Intent-to-Treat (ITT) population will be used for all baseline and demographic summaries and listings unless otherwise specified. Summaries will be reported by treatment group labeled as specified in [Table 2-1](#) and for all subjects and listings will be reported by treatment group to assess baseline comparability. No inferential statistics will be provided.

2.3.1 Patient disposition

A summary of the number of subjects in each of the analysis populations described in [Section 2.2](#) will be provided. A listing of analysis populations in which each subject will be included or excluded will be provided as well.

A summary of study treatment status (octreotide, lapatinib and capecitabine) will be provided. This display will show the number and percentage of subjects who completed all doses of Octreotide, completed 24 weeks of treatment with lapatinib and capecitabine and a summary of the primary reason for discontinuation of study treatment. Reasons for study treatment discontinuation will be presented in the order they are displayed in the eCRF.

A separate table of a summary of study status will be provided with frequency and percentages for patients died and withdrawn from study will be provided. Reasons for withdrawal will be presented in the order they are displayed in the eCRF.

Listing of patient disposition will be provided including details on study treatment discontinuation and study discontinuation.

2.3.2 Protocol deviations

The number (%) of patients in the ITT population with any important protocol deviation will be tabulated by deviation category, total, and by treatment group for the ITT population. All important protocol deviations will be listed and deviations leading to exclusion from per protocol population will be flagged in the listing. The important protocol deviation will be categorized as below as per GSK SOP:

- those who entered the study even though they did not satisfy the entry criteria;
- those who developed withdrawal criteria during the study but were not withdrawn;
- those who received the wrong treatment or incorrect dose;
- those who received an excluded concomitant treatment
- Any study specific procedure or assessment deviation, which the study team determines may compromise subject rights, safety, or well being, or has a significant impact on study conclusions

Protocol deviations are listed / described in the Protocol Deviation Management Plan, (PDMP). All protocol deviations will be summarized and listed. Protocol deviations will be classified by criteria - Deviations are/aren't important or/and Deviations that do/don't require exclusion from per-protocol population.

2.3.3 Basic demographic and background data

Demographics data and background data at baseline (including key efficacy variables) will be summarized by treatment for all Intent-to-Treat subjects (ITT).

Categorical variables will be summarized by frequency counts and percentages.

The category "Missing" will be displayed if data is missing

Continuous variables will be summarized by n (number of subjects with a non-missing value), mean, standard deviation, minimum (Min.), median, and maximum (Max.).

Demographics data summary includes the following variables:

- (continuous) Age (years) at Screening
- (categorical) Age group at Screening:
 - <18 years
 - >= 18 years - <65 years
 - >= 65 years - <75 years
 - >=75 years
- (categorical) Sex
- (categorical) Ethnicity:
- (categorical) Geographic Ancestry
- (continuous) Baseline Height (cm) at Screening
- (continuous) Baseline weight (kg) at Screening

- (categorical) Baseline ECOG performance status at Screening

A by-subject listing of all demographic characteristics will be produced.

2.3.4 Disease history and medical history

Cardiovascular medical history / risk factors assessed at screening, disease characteristic for the primary tumor type under study at screening and biomarker assessment at screening will be summarized and listed.

In addition, prior anti-cancer therapies are summarized.

2.4 Treatments (study treatment, rescue medication, concomitant therapies, compliance)

2.4.1 Study treatment and compliance

A listing of percentage overall compliance for octreotide, lapatinib and capecitabine based on the exposure data will be produced. **Overall compliance (octreotide) is calculated as:**

$$\text{Overall compliance (\%)} = \frac{\text{total cumulative actual dose}}{\text{total cumulative planned dose}} \times 100.$$

where total cumulative planned dose of octreotide will be 80mg if the subject is continuing in the study at the Cycle 2 visit or 40mg otherwise.

Overall compliance (lapatinib) is calculated as:

$$\text{Overall compliance (\%)} = \frac{\text{total cumulative actual dose}}{\text{total cumulative planned dose}} \times 100.$$

where total cumulative actual (or planned) dose is the summation of all actual (or planned) daily doses (mg) of lapatinib in the duration of lapatinib which is last dose date-first dose date +1.

Overall compliance (capecitabine) is calculated as:

$$\text{Overall compliance (\%)} = \frac{\text{total cumulative actual dose}}{\text{total cumulative planned dose}} \times 100.$$

where total cumulative actual (or planned) dose is the summation of all actual (or planned) daily doses (mg/m²) of capecitabine in the duration of lapatinib which is last dose date-first dose date +1.

In addition, summaries of exposure to study medication (octreotide, lapatinib and capecitabine) and dose modifications (e.g., number of dose reductions, escalations, and interruptions) will further characterize compliance. These analyses are described in [Section 2.7.1](#) 'Extent of Exposure'.

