## 5.8. Treatment Compliance

Compliance with treatment with lapatinib and capecitabine will be assessed through querying the subject during the site visits and will be recorded in the source documents and in the eCRF.

A record of the number of lapatinib and capecitabine tablets dispensed to and returned by each subject must be maintained and reconciled with treatment and compliance records. Treatment start and stop dates, including dates for treatment delays and/or dose reductions will also be recorded in the eCRF.

Treatment delays and/or dose reductions will also be recorded by subjects in the DMD. The eCRF and the DMD are considered to be independent source data, and information recorded in the DMD should not be used to supplement information recorded in the eCRF.

Octreotide will be administered to subjects at the study site. Administration will be recorded in the source documents and in the eCRF.

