To determine the efficacy of prophylactic octreotide in reducing the proportion of subjects experiencing diarrhoea of any grade of severity.	Proportion of subjects experiencing diarrhoea of any grade of severity as defined by the NCI-CTCAE, version 4.03, recorded as AEs in the eCRF.
To determine the efficacy of prophylactic octreotide in increasing the time to onset of the first episode of diarrhoea of any grade of severity.	Time to onset of the first episode of diarrhoea of any grade of severity, recorded as an AE in the eCRF.

Objectives	Endpoints
Secondary: Investigator reported	
To determine the effect of prophylactic octreotide on compliance with lapatinib and capecitabine treatment.	Number of lapatinib and capecitabine tablets dispensed and returned, recorded in the eCRF.
To determine the effect of prophylactic octreotide on the efficacy of treatment with lapatinib and capecitabine.	Overall response rate and clinical benefit response measured in accordance with the Response Evaluation Criteria In Solid Tumours (RECIST) version 1.1.
To determine the effect of prophylactic octreotide on the safety and tolerability of cancer treatment.	Proportion of subjects with AEs and SAEs, recorded in the eCRF.
Secondary: Patient reported Diarrhoea Management Diary (DMD)	
To determine the effect of prophylactic octreotide on patient reported diarrhoea.	Patients reporting changes in bowel movements from baseline (frequency and/or consistency), recorded in the DMD.
Quality of Life – FACIT-D	
To determine the effect of prophylactic octreotide on health-related quality of life.	Trial Outcomes Index will be the primary measure; the sub-scales, Total FACT-G score and Total FACIT-D score will be secondary measures.

2 Statistical methods

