2.6.1.4 Study treatment compliance

Inference of the efficacy of prophylactic octreotide will be made by summarising compliance to lapatinib and capecitabine separately by treatment group. Compliance will be derived as described in [Section 2.4.1](#).

A summary of compliance with prophylactic octreotide will be presented. Compliance will be derived as described in [Section 2.4.1](#).

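### Compliance is defined by tablet counts but calculated from exposure records between first and last dose, so the summary used to judge octreotide leaves out treatment given up early

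*SAP*

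**What the plan says.** **Endpoint.** SAP Table 1-3 (section 1.1) gives it as "Number of lapatinib and capecitabine tablets dispensed and returned, recorded in the eCRF", and protocol Table 7 agrees. SAP section 4 describes Table 1-3 as the reduced endpoint list for the abbreviated report, so this endpoint was kept. Protocol 5.8 supplies the data: "A record of the number of lapatinib and capecitabine tablets dispensed to and returned by each subject must be maintained".

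**Calculation.** SAP 2.4.1 works from exposure data: "A listing of percentage overall compliance for octreotide, lapatinib and capecitabine based on the exposure data will be produced". Compliance is 100 times cumulative actual dose over cumulative planned dose. For lapatinib, both are sums of daily doses "of lapatinib in the duration of lapatinib which is last dose date-first dose date +1". For capecitabine, they are sums "of capecitabine in the duration of lapatinib which is last dose date-first dose date +1". For octreotide, the planned total is fixed instead, at "80mg if the subject is continuing in the study at the Cycle 2 visit or 40mg otherwise".

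**Use.** SAP 2.6.1.4 refers back to this derivation and states: "Inference of the efficacy of prophylactic octreotide will be made by summarising compliance to lapatinib and capecitabine separately by treatment group".

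No tablet-count calculation appears in the SAP. Planned daily dose is not defined as either the starting dose or the dose after modification. SAP section 4 does not mention the change of data source, although protocol 9.3.5 says deviations from the protocol's analysis plan will be documented in the analysis plan.

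**The concern.** The endpoint and the derived variable measure different things. Separately, the first-to-last-dose window removes all time after permanent discontinuation from both numerator and denominator. A subject who gives up lapatinib and capecitabine because of diarrhoea is judged only on the days before giving up. A subject who tolerates a hold and carries on has the hold counted, if planned dose means the full protocol dose.

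The compliance objective asks whether prophylaxis helps patients keep taking their cancer treatment. If octreotide worked by turning discontinuations into short interruptions, this measure would not credit it and could, in some patterns, rank the arms the wrong way round. Section 2.4.1 does not treat octreotide in this way: a subject still in the study at Cycle 2 who skips the second injection scores 40/80 = 50%.

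**Working it through.** The documents state no compliance figure, so there is nothing to reproduce. The check applies the SAP formula to simple lapatinib histories.

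**Inputs from the documents**
- Lapatinib 1250 mg daily as 5 tablets (protocol 5.1.1).
- Study period 24 weeks = 168 days; primary period 9 weeks = 63 days.
- Interruption of up to 14 days (protocol Table 10).
- Withdrawal for diarrhoea on lapatinib plus capecitabine: 5% in EGF100151, <1% in EGF111438 (protocol 1.1).
- Control incidences of Grade 2 or higher diarrhoea: 20% and 32% (SAP 3.1).

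**Assumptions, not in the documents:** the stop day, the days missed before stopping, and the share of subjects affected.

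**Single subjects.** Compliance = 100 × dosed days / days from first to last dose, with planned = full protocol dose.

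| History | SAP formula | Over 168 days |
|---|---|---|
| Stops day 21, none missed | 21/21 = 100% | 21/168 = 12.5% |
| Stops day 42, none missed | 42/42 = 100% | 42/168 = 25% |
| Stops day 42, 7 missed | 35/42 = 83.3% | 35/168 = 20.8% |
| Stops day 42, 14 missed | 28/42 = 66.7% | 28/168 = 16.7% |
| Completes with one 14-day hold | 154/168 = 91.7% | 154/168 = 91.7% |

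If planned means the dose after protocol-directed holds, the last row becomes 154/154 = 100%.

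**Arm means.** Let a share f be affected. Affected controls stop at day 42 with nothing missed. Affected octreotide subjects hold for 14 days and continue. Everyone else scores 100%.

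| f | SAP formula: control vs octreotide | Over 168 days: control vs octreotide |
|---|---|---|
| 20% | 100 vs 98.3 | 85.0 vs 98.3 |
| 30% | 100 vs 97.5 | 77.5 vs 97.5 |
| 32% | 100 vs 97.3 | 76.0 vs 97.3 |

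For f = 30%: 0.70 × 100 + 0.30 × 91.7 = 97.5, and 0.70 × 100 + 0.30 × 25 = 77.5.

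**When the ranking reverses.** The stoppers must score above 91.7%, so they must have missed fewer than 42 × 14/168 = 3.5 days. At f = 30%, 3 missed days give 97.9 vs 97.5 (reversed) and 4 give 97.1 vs 97.5 (not reversed).

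**Plausible size.** The gap between a clean stopper and a persister with a full 14-day hold is 100 − 91.7 = 8.3 points. With 5% affected, the arm mean shifts by 0.05 × 8.3 = 0.4 points; below 1%, by less than 0.1. SAP section 1 reports 62 enrolled. If these split evenly, 5% of 31 is about 1.6 subjects per arm.

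**Would tablet counts alone cure it?** No. A stop at day 21 means 5 × 21 = 105 tablets dispensed and none returned: 105/105 = 100%. A stop at day 50 after three 105-tablet supplies means 315 dispensed and 65 returned. Over the subject's own dosing dates that is 250/(5 × 50) = 100%. Only dividing by all tablets dispensed lowers it, to 250/315 = 79.4%.

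**A fixed nine-week period.** A stop at day 42 gives 42/63 = 66.7%. A 14-day hold within the period gives 49/63 = 77.8%. The abandoned days now count.

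**The case against.** Excluding days after discontinuation is an ordinary on-treatment definition of compliance; persistence is a separate quantity, and the SAP reports it elsewhere. Section 2.3.1 tabulates 24-week completion and reasons for stopping, 2.7.1.2 categorises time on treatment, and 2.7.5 summarises adverse events leading to discontinuation of each drug. Section 2.4.1 itself says exposure and dose-modification summaries will add to the picture. The comparison has no test and sits in an abbreviated report of a trial stopped for futility. All of this stands, and it limits the consequence. It does not align the endpoint with its derivation, and 2.6.1.4 rests its inference on the compliance figure rather than on those tables.

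Three stronger readings are tempting, and the documents do not support them.
- **Early stoppers simply score 100%.** They do so only if every planned dose up to the last was taken. For capecitabine, protocol Table 11 places holds before discontinuation for repeated Grade 2 or 3 events, so stops under that rule follow earlier holds.
- **The high score comes from using exposure records.** It comes from the window; tablet counts over a subject's own dosing dates give the same 100%.
- **The lapatinib-based window penalises stopping capecitabine alone.** Protocol 4.3.2 and 5.9 require both drugs to stop permanently together. Because doses may be adjusted independently, last-dose dates could still differ after a final hold. That is a reason to correct the wording, not evidence of material bias.

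One objection also shapes the remedy. Scoring zero after every discontinuation over 24 weeks would count progression as lost treatment. Median investigator-assessed time to progression on the combination was 23.9 weeks (protocol Table 1), so about half of subjects could be affected for reasons unrelated to diarrhoea.

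**Conclusion.** The mismatch between endpoint and calculation is plain on the page, as are the undefined planned dose, the lapatinib-based capecitabine window and the silence of SAP section 4. The window also leaves treatment given up early out of a figure used to infer octreotide efficacy.

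The numerical effect is probably small: about 0.4 points at 5% withdrawal for diarrhoea, taking clean stoppers against persisters with a full 14-day hold, and less than 0.1 at under 1%. A reader might infer that the comparison will have the wrong sign. The documents do not show that. Reversal needs planned dose to mean the full protocol dose, few missed days before stopping (fewer than 3.5 in the illustration), and an imbalance in stopping that no source in the documents provides. It is a possibility worth removing because removing it is cheap.

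**What to change.** 1. In SAP 2.4.1, derive lapatinib and capecitabine compliance from the collected counts: (dispensed − returned) / tablets prescribed after any protocol-directed hold or reduction, each drug over its own first-to-last dosing dates. If exposure data are kept instead, amend Table 1-3, define planned dose, correct the capecitabine window and record the change in section 4.
2. Add, from exposure data, dose delivered as a percentage of the full protocol dose over weeks 0-9. Count zero after discontinuation for toxicity or subject decision, and show discontinuation for progression or death separately. Protocol 4.3.2 already requires the primary reason to be recorded. Read any 0-24 week version beside the reasons for discontinuation.
3. Base the inference sentence in 2.6.1.4 on both measures.

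The cost is SAP wording, reprogramming one derived variable and adding another. Protocol 5.8 already requires the tablet counts. The downsides are that unreturned packs need a missing-count rule and the percentages will look slightly less favourable.

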All subjects with episodes of diarrhoea will be encouraged to follow the GSK diarrhoea management guidelines for subjects receiving lapatinib ([Appendix 1](#)). In subjects randomised to receive octreotide, episodes of mild diarrhoea which occur following the first dose of octreotide LAR should be managed in accordance with the diarrhoea management guidelines. The use of octreotide in the s.c. formulation for the management of diarrhoea refractory to treatment with loperamide is not excluded. Investigators should use their clinical judgement concerning the use of octreotide s.c. in subjects randomised to receive treatment with octreotide LAR, particularly during Week 2 through to Week 12 of treatment with lapatinib and capecitabine, when circulating concentrations of octreotide should already be within the clinically effective range.

Subjects who report constipation with a severity of NCI CTCAE Grade 2 and above ([Table 9](#)) following the first dose of octreotide LAR must not receive the second dose of octreotide LAR, but will continue to receive treatment with lapatinib and capecitabine as scheduled.

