### **4.3. Permanent Discontinuation from Study Treatment and Subject Completion Criteria**

#### **4.3.1. Discontinuation from Treatment with Octreotide**

Subjects randomised to receive octreotide must be given one 0.1mg dose of the standard formulation of octreotide s.c. to assess tolerability at least one hour before the first dose of the LAR formulation is administered. Subjects who show any evidence of intolerability to octreotide administered s.c. **must not** receive treatment with the LAR formulation; these subjects should receive treatment with lapatinib and capecitabine and should not be withdrawn from the study.

Subjects randomised to receive octreotide will be given prophylactic octreotide (Sandostatin LAR) 40mg 7 days before the start of treatment with lapatinib and capecitabine and again 28 days later. Episodes of mild diarrhoea which occur following treatment with octreotide LAR should be managed in accordance with the diarrhoea management guidelines ([Appendix 1](#)). The use of octreotide in the s.c. formulation for the management of diarrhoea refractory to treatment with loperamide is not excluded. Investigators should use their clinical judgement concerning the use of octreotide s.c. in

subjects randomised to receive treatment with octreotide LAR, particularly during Week 2 through to Week 12 of treatment with lapatinib and capecitabine, when circulating concentrations of octreotide should already be within the clinically effective range. Subjects who report constipation with a severity of NCI CTCAE Grade 2 and above (Table 9) or other adverse events which are considered likely to be related to octreotide treatment following the first dose of octreotide LAR must not receive the second dose of octreotide LAR, but should continue to receive lapatinib and capecitabine and should not be withdrawn from the study.

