#### **5.3.1. Octreotide Dosage and Administration**

Octreotide in the formulation for s.c. injection will be administered as a 0.1mg dose (1mL) at the study site to assess tolerability at least one hour before the first 40mg dose of the LAR formulation is administered. The LAR formulation must not be administered to any subjects who show signs or symptoms of intolerance to octreotide following administration of the 0.1mg s.c. dose.

The 40mg dose of the LAR formulation will be given as two 20mg doses, each of approximately 2.5mL. The mixing instructions for this formulation should be followed carefully to ensure the suspension is properly prepared. Octreotide in the LAR formulation will be administered at the study site 7 days prior to starting the first cycle of treatment with lapatinib and capecitabine, and repeated 28 days later.

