- Not mandatory at these visits, but should be conducted in accordance with local clinical practice, at the time of a scheduled 3 weekly visits when possible.
- PROs are the FACIT-D and the DMD.
- Week -1 baseline PROs to be completed prior to randomisation, before the octreotide 0.1mg s.c. tolerability assessment dose.
- If clinically indicated, in accordance with the Lapatinib SPC.
- First dose of octreotide LAR to be given 7 days before start of Cycle 1 treatment with lapatinib and capecitabine. Subjects must receive octreotide 0.1mg s.c. at least one hour before the first dose of octreotide LAR to assess tolerability.
- Visits at the start of Cycle 2 and Cycle 4 are mandatory.** Visits at the start of Cycle 3, 5, 6, 7 and 8 are not mandatory; visits every 3 weeks would be preferred, but may be adapted to match local practice.
- Week 0 baseline PROs to be completed before the first dose of lapatinib and capecitabine is administered.
- 
- Cycle 2 to be started 21 days ( $\pm 2$  days) after the start of Cycle 1. Other cycles should be started within  $\pm 4$  days of the 3 weekly treatment cycle intervals.
- Second dose of octreotide LAR to be given 28 days ( $\pm 2$  days) after first dose of octreotide LAR.
- After 24 weeks treatment with lapatinib and capecitabine. Investigators should continue to treat subjects with lapatinib and capecitabine beyond 24 weeks in accordance with local clinical practice.
- Serious adverse events and other safety data as described in Section 7.4 should be reported for all subjects who continue treatment with lapatinib and capecitabine beyond the 24 week end of study assessment.
- If more than 12 weeks since the screening cardiac function assessment.

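### Octreotide compliance is scored against 80 mg even when the protocol forbids a dose, so subjects treated exactly per protocol score 50% or 0%

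*SAP*

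**What the plan says.** SAP 2.4.1 defines overall octreotide compliance as cumulative actual dose over cumulative planned dose, times 100. On the denominator it says that "total cumulative planned dose of octreotide will be 80mg if the subject is continuing in the study at the Cycle 2 visit" "or 40mg otherwise". Nothing else about the subject enters the rule. The result is listed, and SAP 2.6.1.4, among the investigator-reported secondary endpoints, adds: "A summary of compliance with prophylactic octreotide will be presented".

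The protocol sets the dosing rules that this denominator has to match:

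- Section 5.3.1: "The 40mg dose of the LAR formulation will be given as two 20mg doses". Table 16: "Second dose of octreotide LAR to be given 28 days" after the first, in Cycle 2.
- Section 5.3.1, on the 0.1 mg test dose: "The LAR formulation must not be administered to any subjects who show signs or symptoms of intolerance to octreotide". Section 4.3.1 has these subjects go on to lapatinib and capecitabine without being withdrawn.
- Section 3.1: subjects with Grade 2 or higher constipation after the first LAR dose "must not receive the second dose of octreotide LAR, but will continue to receive treatment with lapatinib and capecitabine as scheduled". Section 4.3.1 states the same bar, beginning "Subjects who report constipation with a severity of NCI CTCAE Grade 2 and above", and extends it to other adverse events thought likely to be octreotide-related. Section 5.9 repeats the extended bar.
- Section 5.9 allows neither reduction nor delay of octreotide, so each planned LAR dose is either 40 mg or nothing.

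**The concern.** The measure is called compliance, so a reader will take it as adherence to the planned regimen. The rule asks only whether the subject is still on study at Cycle 2. It does not ask whether the protocol allowed the dose. Subjects barred from LAR are meant to stay on study, so those who reach Cycle 2 carry the 80 mg denominator.

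The rule is also uneven in its own terms. It takes dose 2 out of the denominator when a subject has left and can no longer receive it, but leaves it in when the protocol itself rules the dose out.

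The trial stopped for futility, so whether octreotide was delivered as intended is a natural question about the result. A mean below 100% could come from required omissions or from lapses at the site, and the summary as defined cannot show which.

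**Working it through.** **Inputs.** One LAR dose is 2 x 20 mg = 40 mg (Protocol 5.3.1). Two doses are 2 x 40 = 80 mg. Both SAP denominators, 80 mg and 40 mg, are reproduced. The bars on dosing are in Protocol 3.1, 4.3.1, 5.3.1 and 5.9.

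**Formula.** Compliance (%) = actual dose / planned dose x 100.

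| Subject in the octreotide arm | Actual (mg) | SAP planned (mg) | SAP score | Permitted (mg) | Score against permitted |
|---|---|---|---|---|---|
| Both LAR doses given | 80 | 80 | 100% | 80 | 100% |
| Dose 2 forbidden, on study at Cycle 2 | 40 | 80 | 50% | 40 | 100% |
| Dose 2 missed with no protocol reason, on study at Cycle 2 | 40 | 80 | 50% | 80 | 50% |
| Test-dose intolerant, on study at Cycle 2 | 0 | 80 | 0% | 0 | 0/0, undefined |
| Dose 1 given in full, left before Cycle 2 | 40 | 40 | 100% | 40 | 100% |
| Test-dose intolerant, left before Cycle 2 | 0 | 40 | 0% | 0 | 0/0, undefined |

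Counting the 0.1 mg test dose as drug given would change the fourth row only to 0.1/80 = 0.125%.

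Rows two and three are the core of the point. One subject was treated as the protocol requires and the other was not, and the SAP gives both 50%.

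**Effect on the arm mean.** Let f be the share barred from dose 2 and g the share intolerant of the test dose. Assume all of these are on study at Cycle 2 and everyone else scores 100%. The SAP mean is then 100 - 50f - 100g. The documents give neither share, so these values are assumptions:

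- f = 10%, g = 0: 100 - 5 = 95%
- f = 20%, g = 0: 100 - 10 = 90%
- f = 10%, g = 2%: 100 - 5 - 2 = 93%
- f = 20%, g = 5%: 100 - 10 - 5 = 85%

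The true number of deviations is zero in every line.

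**Per subject.** SAP section 1 reports 62 enrolled. Assuming an even split, the arm has 62/2 = 31 subjects. Each required omission of dose 2 lowers the mean by 50/31 = 1.6 points, and each test-dose-intolerant subject lowers it by 100/31 = 3.2 points.

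**The case against.** The strongest reply is that the ratio is a legitimate measure of dose delivered, that SAP 2.4.1 uses the same form for lapatinib and capecitabine, and that other outputs fill the gap. SAP 2.4.1 itself says that exposure and dose-modification summaries will add to the picture of compliance. SAP 2.7.1.1 counts subjects by number of 20 mg administrations and by missed doses. SAP 2.7.1.2 lists missed octreotide doses. SAP 2.3.1 reports how many completed all octreotide doses, with a primary reason for discontinuing study treatment. SAP 2.7.5 summarises adverse events that led to stopping octreotide. Nothing is tested on the compliance figure.

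Much of this stands. The dose counts are already planned, and a determined reader could recover part of the explanation. It does not repair the summarised figure, for two reasons.

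- The 2.7.1.1 summary counts missed doses but gives no reasons. The reason summaries in 2.7.1.2 concern lapatinib and capecitabine.
- The exposure and adverse event tables use the Safety population. SAP 2.2 moves a test-dose-intolerant subject who took lapatinib or capecitabine into the no-octreotide arm for safety, so these tables do not show that subject in the octreotide arm. SAP 2.6.1.4 names no population, and ITT is the natural reading under 2.6.1. Protocol 9.3.5.1.2 asks for ITT and m-ITT. The m-ITT set would drop the 0% scores but keep the 50% scores.

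A reader might also infer that early dropouts are wrongly rewarded with 100%. They are not: a subject who received dose 1 in full and left before Cycle 2 had everything due by then, and scores 40/40 under either rule.

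**Conclusion.** The planned-dose rule in SAP 2.4.1 misstates compliance for subjects whom the protocol bars from LAR and keeps on study. They score 50% or 0% without any deviation, and a required omission of dose 2 is merged with a true miss. On the assumed ranges above, the arm mean is understated by 0 to 15 points. The actual amount depends on how many subjects were barred, which the documents do not report.

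The point is limited to a descriptive secondary summary. The ITT chi-square test of the primary endpoint does not use this figure. A reader might go further and infer that the summary would make under-treatment look like the cause of a null result when octreotide was really not tolerated. The documents do not support that: they give no rate of dose 2 omission or test-dose intolerance, and poor tolerability cannot be presumed.

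**What to change.** In SAP 2.4.1, define planned octreotide dose for compliance as the LAR doses the protocol permitted for that subject while on study, 40 or 80 mg. Leave test-dose-intolerant subjects out of the ratio, which would be 0/0, and report them as a separate count. If actual dose over 80 mg is still wanted, keep it under the label of dose delivered.

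Name the population in SAP 2.6.1.4 as the randomised octreotide arm (ITT). For that arm, extend the dose counts of 2.7.1.1 with the reason for each omitted LAR dose: test-dose intolerance, constipation, other octreotide-related adverse event, withdrawal, or missed with no protocol reason.

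The cost is a short change to the SAP text and one extra small table. Octreotide administration and adverse events are already recorded in the eCRF, although the documents do not show a dedicated field for the reason a dose was omitted, so some reasons may have to be derived. The trade-off is that the compliance figure no longer measures total drug received, which is why the dose-delivered ratio may be worth keeping beside it. No dosing rule changes.
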